7.2 Archiving

In line with the principles of Good Clinical Practice and UK Clinical trial Regulations guidelines, at the end of the study, data will be securely archived for a minimum of ten years. Arrangements for confidential destruction will then be made. If a subject withdraws consent for their data to be used, it will be confidentially destroyed immediately.

8. Statistical considerations

8.1 Power analysis

This study will aim to include all CD cases with MRE imaging since 2015; the estimated sample size is therefore 1100 cases.

To our knowledge, there are no studies comparing the sensitivity and / or specificity of MRE scans with gold standard dedicated MRI for the detection of sacroiliitis. However, there have been some studies comparing CT imaging with MRI and these found MRI to be up to 17% more sensitive for the detection of sacroiliitis than CT [48, 49].

Although MRE is expected to be more sensitive at detecting evidence of sacroiliitis than CT, our power calculation is based on the conservative estimate that MRE will detect at $\geq 60\%$ (sensitivity) of

the cases of sacroiliitis, when compared with the gold standard dedicated axial MRI scan. Therefore with 80% power and a two-tailed alpha of 0.05, it is estimated that ≥ 60 control subjects (MRE normal) will be required for the study. It is estimated that a sample of >60 cases (with abnormal MRE scans) would be needed since the sample size required to assess specificity for a screening test is less than that of sensitivity. Case and controls will be recruited in a ratio of 1:1. From the 1100 MRE scans already performed, it is expected that $\geq 90\%$ will have a diagnosis of CD, i.e. 990 subjects. We estimate that $\geq 50\%$ of postally invited participants will consent to participate in the study, giving approximately 445 MRE scans for review.

The two previous studies assessing IBD patients for evidence of sacroiliitis using MRE imaging estimated the prevalence to be 16.7% and 15% [27, 28]. We therefore estimate to recruit ≥ 66 subjects with positive MRE scans (cases) and ≥ 66 matched controls. This is a conservative estimate, greater than the minimum number needed to recruit.

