The SPARCC MRI index criteria score will then be used to determine the validity of our specifically designed scoring system for the dedicated axial MRI scans. The scores of the dedicated MRI scans will then be compared to the MRE scores for each patient to determine the validity of using MRE as a screening tool for axSpA in patients with CD. The sensitivity, specificity and area under the ROC curve of using MRE as a screening tool will also be determined.

If an unexpected finding is identified, such as a fracture or potential malignancy, then the gastroenterology team will be informed and appropriate onward referrals and communication (in-person or telephone, as deemed clinically appropriate) to the patient will be made.

5. Study subject selection

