Subjects (including those with a known diagnosis of SpA) without evidence of axSpA on MRE will be contacted by the gastroenterology team (by letter) to inform them of the results and will also be advised that they may be invited to enter the study as a control subject. Once the cases have been identified and enrolled, control subjects will then be randomly selected (age and sex-matched in a case : control ratio of 1:1) to enter the research element of the study. The gastroenterology team will then write to these subjects to invite them to enter the study, accompanied by a PIS and a reply slip (study interest form) with a stamped-addressed envelope to permit the subject to express if they do or do not wish to participate further. Any CD subjects with a history of SpA who have been selected as a potential control subject will be sent a separate invitation letter, PIS and reply slip (study interest form) by the gastroenterology team.

During the clinic consultation for both cases and controls, the research study will be discussed further and the subject will be provided with the opportunity to ask any questions they may have regarding the study. If the subject subsequently agrees to take part in the study, then inclusion and exclusion criteria will be assessed and informed written consent will be taken.

6. Study schedule

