8.2 Statistical analysis

Statistical input has been sought from the University of Cambridge Statistics Clinic (PhD student [name] and his supervisor [name]) and will be supported by [name]. Inter- and intra-rater reliability testing will be performed for the MRE and axial MRI assessments using intra-class correlation coefficients (ICC). The proportion of CD cases with evidence of axSpA on MRE imaging who fulfil diagnostic criteria for axSpA will be expressed as a percentage. Further descriptive analyses will also be performed on study participants. Due to the possible preponderance of patients with axial pain willing to participate in the study and therefore selection bias, we will not be able to calculate the true prevalence of axSpA in CD patients.

As it is expected that the majority of data collected will be count data with an excess of zero-values, a zero-inflated Poisson (ZIP) regression model will be used to test for association between the presence of axSpA, MRE score, PROMs, clinical indices, site of CD and blood biomarkers. In addition, ZIP regression will be used to test for association between MRE scores and those of dedicated axial MRI scans. Zero-inflated binomial regression will be used as appropriate, where the mean approximates the variance. Two-tailed tests will be performed, and the alpha set at 0.05.

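### The 80% power claim in section 8.1 has no comparison value and is attached to MRE-defined groups that are not the denominators of sensitivity or specificity

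*Combined protocol and SAP*

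**What the plan says.** The aim (sections 1.2 and 3.1) is the sensitivity and specificity of MRE for axSpA, with dedicated axial MRI plus clinical assessment as the reference.

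Section 8.1 says "our power calculation is based on the conservative estimate that MRE will detect at" 60% or more of "the cases of sacroiliitis, when compared with the gold standard dedicated axial MRI scan". It then states "with 80% power and a two-tailed alpha of 0.05, it is estimated that ≥ 60 control subjects (MRE normal) will be required". A further requirement of more than 60 MRE-abnormal cases is justified by the remark that specificity needs fewer subjects than sensitivity; no expected specificity is given. The yield paragraph ends: "We therefore estimate to recruit ≥ 66 subjects with positive MRE scans (cases) and ≥ 66 matched controls".

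The groups are defined by the MRE result (sections 1.5 and 4.1). Section 5.2.2.2 adds that "control subjects will then be randomly selected (age and sex-matched in a case : control ratio of 1:1").

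On analysis, section 4.3.3 promises: "The sensitivity, specificity and area under the ROC curve of using MRE as a screening tool will also be determined". Section 8.2 does not say how. Its only accuracy-type quantity is this: "The proportion of CD cases with evidence of axSpA on MRE imaging who fulfil diagnostic criteria for axSpA will be expressed as a percentage".

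**The concern.** A sample size for a test of one proportion needs an expected value and a value to test against. Section 8.1 gives only the first, so its 80% power refers to no defined test.

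The second problem remains whatever comparison was intended. Sensitivity is TP/(TP+FN): the true positives lie in the MRE-positive group and the false negatives in the MRE-negative group. Specificity likewise draws on both groups. Fixing the numbers of MRE-positive and MRE-negative subjects gives PPV and NPV directly; the denominators of sensitivity and specificity become random. A requirement for sensitivity therefore cannot be expressed as a number of MRE-normal controls.

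This is the only power statement for the primary aim. The precision of the sensitivity estimate depends on a handful of false negatives among about 66 controls. MRE-positives are also heavily over-represented in a 1:1 sample, so an unweighted calculation would flatter the screening tool.

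**Working it through.** **1. Can 60 be reproduced?** The stated inputs (two-sided alpha 0.05, power 80%, sensitivity 0.60) do not determine a number. The one-sample formula is n = [(1.96√(p0(1−p0)) + 0.8416√(p1(1−p1)))/(p1−p0)]². With a comparison supplied:

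- null 0.42, alternative 0.60: 58.7
- null 0.60, alternative 0.77 (adding the 17% that section 8.1 cites for MRI against CT): 59.8
- null 0.50, alternative 0.60: 193.8

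So about 60 is obtainable, but only with an undeclared comparison. It would then count MRI-positive subjects, not MRE-normal ones.

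**2. What the design delivers.** Inputs from section 8.1: N = 445 scans (used as stated), q = 0.15 MRE-positive, 66 verified per group. Assumptions: true sensitivity S = 0.60; PPV 0.5, 0.8 or 0.9 (not in the documents).

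- Proportion of MRE-negatives who are reference-positive: FOR = q·PPV·(1−S)/[S(1−q)].
- Expected false negatives among controls: 66·FOR.
- Var(logit sensitivity) = (1−PPV)/(66·PPV) + (1−FOR)/(66·FOR) + 1/[N·q(1−q)].
- Effective sample size: 1/(0.24·Var).

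At PPV 0.8: FOR = 0.15×0.8×0.4/(0.6×0.85) = 0.0941, giving 6.2 false negatives. Var = 0.0038 + 0.1458 + 0.0176 = 0.167 and SE = 0.409. The 95% CI is expit(0.405 ± 1.96×0.409) = 0.402 to 0.770. The false-negative term is most of the variance.

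| | PPV 0.5 | PPV 0.8 | PPV 0.9 |
|---|---|---|---|
| FOR | 0.0588 | 0.0941 | 0.1059 |
| False negatives in 66 controls | 3.9 | 6.2 | 7.0 |
| Var(logit sensitivity) | 0.275 | 0.167 | 0.147 |
| Effective n for sensitivity | 15.1 | 24.9 | 28.3 |
| 95% CI, sensitivity | 35-81% | 40-77% | 41-76% |
| Specificity (95% CI) | 91.4% (88-94) | 96.3% (94-98) | 98.1% (96-99) |

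The specificity CI uses Var(logit) = PPV/[66(1−PPV)] + FOR/[66(1−FOR)] + 1/[N·q(1−q)].

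**3. Power for the two comparisons in step 1.** With d the difference in logits and the SE recomputed at each sensitivity, Wald power is Φ(d/SE_alt − 1.96) and null-variance power is Φ((d − 1.96·SE_null)/SE_alt).

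| | PPV 0.5 | PPV 0.8 | PPV 0.9 |
|---|---|---|---|
| 0.42 vs 0.60, Wald | 28% | 43% | 47% |
| 0.42 vs 0.60, null-variance | 49% | 65% | 70% |
| 0.60 vs 0.77, Wald | 18% | 26% | 29% |
| 0.60 vs 0.77, null-variance | 39% | 50% | 54% |

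**4. Unweighted analysis.** Crude sensitivity is PPV/(PPV+FOR). PPV cancels, leaving 1/[1 + q(1−S)/(S(1−q))] = 1/(1 + 0.1176) = 0.895 at every PPV. At PPV 0.8 this is 52.8 of 59.0, with a Wilson 95% CI of about 79-95%, which excludes the true 60%.

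**The case against.** **The figure is not shown to be wrong.** A null of 0.60 against 0.77 returns 59.8, and both ingredients appear in section 8.1, so the input may simply be unlabelled. That is possible. But the plan presents 17% as a difference between MRI and CT and calls 60% the estimate, not the null. Even if that was the calculation, it counts MRI-positive subjects, so the denominator error stands.

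**A precision target also gives about 60.** A half-width of 12.5 points at 60% needs 59.0. True, but a precision target carries no power, so it cannot be the source of an 80% power claim.

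**The shortfall depends on chosen inputs.** This is fair: PPV is assumed, and the Wald and null-variance results differ by about 20 points. Section 8.1 also cites 16.7% positive, about 74 of 445. With 74 plus 74, null-variance power for 0.42 vs 0.60 rises to 73% and 77% at PPV 80% and 90%; both comparisons remain below 80% at every PPV considered. A null of 0.40 does pass (81% and 85%), but it needs only 48 subjects and so does not explain 60.

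**The plan never says it will analyse unweighted.** Correct; the bias is conditional. Nothing in the plan prevents it either.

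**The proposed intervals are approximate.** This stands. They rest on 4 to 7 expected events, and a simulation of the weighted estimator at PPV 50% gave a central 95% sampling range of 0.39-0.89, against the 35-81% above. The plan also gives no age bands for matching, and weighting by MRE result, age and sex does not correct for who consents to the second stage.

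**Conclusion.** The concern holds. The stated 80% power is not a property of this design: no comparison is given, and the numbers are attached to groups that are not the denominators of sensitivity or specificity. Under the two comparisons examined, power is 18-70% at the plan's 15% yield, and the effective sample size for sensitivity is 15 to 28 rather than 60. These sizes rest on a true sensitivity of 60%, PPV between 50% and 90%, and verification of all 66 expected MRE-positives. The two errors themselves do not depend on those assumptions. Enrolment follows the yield of MRE-positive scans, so the number recruited need not change. What must change is the claim made for it and the missing estimator for the primary aim.

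**What to change.** 1. **Section 8.1.** Delete the 80% power claim and the required numbers tied to the MRE-normal and MRE-abnormal groups. State that the number of cases is the expected yield (about 66 of about 445), with 1:1 matched controls, and give the expected precision from the first table in the working. Label it approximate and possibly optimistic: it ignores the matching and assumes every expected MRE-positive is verified. With 50 plus 50 verified and PPV 80%, the interval for sensitivity widens to about 38-79%.
2. **Section 8.2.** Specify that sensitivity and specificity will be weighted back to the screened cohort by MRE result, with MRE-negatives weighted within the age and sex matching strata. Define the age bands. Acknowledge that second-stage non-participation is not corrected by these weights.
3. **If a test is wanted,** state the null value and the power this design gives for it.

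The cost is a reworded section 8.1 and a sentence or two in section 8.2. The stated precision becomes less favourable. No patients or scans are added; the weights need only the MRE result, age and sex of screened subjects, which scoring and matching already require.

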1.5 Study group

The ProSpA-CD study will be divided into two parts:

ProSpA-CD-Screen Phase: Review of the patients MRE scan for evidence of axSpA

The gastroenterology team ([name]) at Cambridge University Hospitals (CUH) will write to approximately 1100 patients with a diagnosis of CD (male and female patients aged 18 years or above) who have had a MRE scan since 2015, asking for their consent to retrospectively review the MRE scans for evidence of axSpA. CD subjects with a known diagnosis of SpA (AS, axSpA, eSpA or

psoriatic arthritis) will be eligible and invited to enter the study. Subjects who consent to this will then have their MRE scans reviewed for this purpose.

ProSpA-CD-Assess Phase: Clinical assessment of case and control subjects for evidence of axSpA in the clinic setting

Patients with lesions on their MRE scan consistent with axSpA (regarded as 'cases'), but who do not have a known diagnosis of SpA, will be referred for further clinical assessment in the NHS rheumatology spondyloarthritis (SpA) clinic for evidence of axSpA ([name] NHS SpA clinic, but assessed by [name] in a supernumerary capacity). Patients will also be invited to participate in the ProSpA-CD-Assess phase of the study at this stage.

CD subjects with a known diagnosis of SpA who are already under review by rheumatology and who have lesions on MRE consistent with axSpA will be considered as cases but will instead be invited to attend the rheumatology SpA research clinic to be assessed for axSpA as this will be considered outside of their routine NHS care ([name] research clinic, but assessed by [name] in a supernumerary capacity).

CD subjects (including those with a known diagnosis of SpA) who had consented to have their MRE scans reviewed, but do not have evidence of axSpA on MRE will also be invited to participate in this phase of the study as 'control' subjects and consenting subjects will be referred for further clinical assessment in the rheumatology SpA research clinic for evidence of axSpA ([name] research clinic, but assessed by [name] in a supernumerary capacity). Cases and controls will be matched for sex and age, with a cases : control ratio of 1:1.

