5.2 Recruitment, consent and randomisation processes

5.2.1 Recruitment

5.2.1.1 Recruitment for the ProSpA-CD-Screen phase:

The gastroenterology team will write to patients with CD who have had MRE imaging since 2015 (estimated to be approximately 1100 patients) to ask them for consent to review their MRE imaging for evidence of axSpA. CD subjects with a known diagnosis of SpA will be eligible and invited to enter the study. Subjects who consent to this will then have their MRE imaging reviewed by a musculoskeletal radiology specialist registrar ([name]) and a rheumatology specialist registrar ([name]).

5.2.1.2 Recruitment for the ProSpA-CD-Assess phase:

Patients with lesions consistent with axSpA on the MRE (and no known diagnosis of SpA) will be informed by telephone and letter by the gastroenterology team and then be referred to [name] NHS SpA clinic *as per* standard of care. They will also be invited to enter the ProSpA-CD-Assess phase of the study at that time and consent will be taken during the clinic encounter.

CD subjects with a known diagnosis of SpA who are already under the care of a rheumatology team and have lesions on MRE consistent with axSpA will also be contacted by telephone and letter by the gastroenterology team. However, since they are already receiving standard NHS care for their SpA, they will be sent a separate invitation letter, PIS and reply slip (study interest form) by the gastroenterology team to attend the rheumatology SpA research clinic for assessment of axSpA by [name] outside of their routine NHS care. Informed consent for study participation will be performed at the start of the consultation.

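### Section 8.1's own inputs give 495 scans for review, not about 445, and its 66 or more recruited cases allow for no loss at second consent or dedicated MRI

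*Combined protocol and SAP*

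**What the plan says.** Section 8.1 opens by treating 1100 as CD cases: "This study will aim to include all CD cases with MRE imaging since 2015; the estimated sample size is therefore 1100 cases". Later in the same section the 1100 are MRE scans already performed, of which at least 90% "will have a diagnosis of CD, i.e. 990 subjects". It then assumes that at least 50% "of postally invited participants will consent to participate in the study, giving approximately 445 MRE scans for review".

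Two earlier MRE studies in inflammatory bowel disease supply prevalences of 16.7% and 15%. From these, 8.1 expects to recruit at least "66 subjects with positive MRE scans (cases") and as many matched controls. Its stated minimum is more than "60 cases (with abnormal MRE scans) would be needed", with at least 60 controls. On the 66 it comments: "This is a conservative estimate, greater than the minimum number needed to recruit".

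The other sections describe the 1100 as patients. Under 1.5 the gastroenterology team "will write to approximately 1100 patients with a diagnosis of CD", 4.1 says the same, and under 5.2.1 it "will write to patients with CD who have had MRE imaging since 2015 (estimated to be approximately 1100 patients").

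Section 5.2.2 sets out two consents: one for review of the existing MRE, and another, taken in clinic, to join the Assess phase as a case or control. The text at the end of section 6 lets a subject decline the dedicated MRI or any other study component.

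**The concern.** There are two faults and one point of wording.

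- **Scan count.** The printed count does not follow from the inputs in the same paragraph, and it feeds directly into the number of cases.
- **Case count.** A number of patients expected to be MRE-positive is presented as a number recruited. The main aim is sensitivity and specificity against dedicated axial MRI with clinical assessment. Only patients who consent a second time and have that MRI contribute to it. The margin over the plan's minimum therefore depends on a rate that the plan does not state. Section 8.3, on missing data, covers only questionnaires.
- **Wording.** The 1100 changes between scans and CD patients.

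Controls are matched 1:1 to enrolled cases. A control who declines can be replaced from the MRE-negative pool, but the number of controls still follows the number of cases.

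**Working it through.** **Inputs, all from 8.1:** 1100 as the starting count; CD share at least 90%; postal consent at least 50%; MRE-positive prevalence 15% and 16.7%; minimum more than 60 cases. Rate of second consent and MRI completion: none stated anywhere.

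**Step 1. The scan count.**
- 1100 x 0.90 = 990, as printed.
- 990 x 0.50 = 495, against about 445 printed. The gap is 50 scans, and 50/495 = 10%.
- Consent rate implied by the printed figure: 445/990 = 44.9%, below the plan's own floor of 50%.
- With a second 0.9: 1100 x 0.90 x 0.90 x 0.50 = 445.5. This matches, but 8.1 states no such factor.

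**Step 2. The 66 cases.**
- 445 x 0.15 = 66.75, which gives the printed 66 or more. No factor below 1 is applied after MRE review.

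**Step 3. Yield from the stated inputs.**
- 495 x 0.15 = 74.25
- 495 x 0.167 = 82.7

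So about 74 to 83 MRE-positive patients are expected before any second-stage loss.

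**Step 4. Second-stage rate needed.** More than 60, as printed, means at least 61 cases with the dedicated MRI done.
- 61/74.25 = 82.2%
- 61/82.67 = 73.8%

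The combined rate of second consent and MRI completion must be about 74% to 82%, so a loss of about 18% to 26% can be absorbed. Taking the threshold as exactly 60 changes this little: 60/74.25 = 80.8% and 60/82.67 = 72.6%. On the printed 445 at 15%, the rate needed is 61/66.75 = 91.4%, a tolerated loss of about 9%.

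**Step 5. Illustration from 495 scans.** The rates below are assumptions; the documents give none.

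| Assumed combined rate | Cases at 15% | Cases at 16.7% |
|---|---|---|
| 70% | 52.0 | 57.9 |
| 80% | 59.4 | 66.1 |
| 90% | 66.8 | 74.4 |

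The minimum is missed at 70%, depends on prevalence at 80%, and is met at 90%.

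**The case against.** The strongest reply is that the slip is on the safe side. Correcting 445 to 495 raises the expected yield. The 90% and 50% are floors, and the 66 uses the lower of the two prevalences. All of this stands: the arithmetic error by itself creates no shortfall.

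Second-stage uptake may also be high. MRE-positive patients without known spondyloarthritis are telephoned and referred to the NHS clinic whether or not they join the study (5.2.1.2). Where the dedicated MRI is clinically indicated, it is done as standard of care (4.3.1). Section 8.2 expects that patients with axial pain may be over-represented. These points stand too, but none is quantified, and research use still needs the second consent.

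A reader might infer that 445 already contains a 10% second-stage loss, since 495 x 0.15 x 0.9 = 66.8. The text does not support this. It labels 445 as scans for review, a count taken before second consent, and the agreement follows merely from multiplying by 0.9 at either point.

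A reader might also infer that 1100 x 50% = 550 scans is the right count. Section 8.1 does not plan on that: it applies its 90% floor first. The 1100 is approximate everywhere outside 8.1 and changes unit within 8.1, so the mismatch with 990 is mainly loose wording.

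**Conclusion.** The point holds in a limited form. As written, 8.1's scan count is wrong by its own inputs: 495, not about 445, unless a first-stage factor has been left out. The 66 or more recruited cases are the expected MRE-positive patients with complete retention assumed. The description as conservative fits the first-stage inputs. It is not supported for recruited cases, because the margin over 60 holds only if about 74% to 82% of MRE-positive patients both consent again and have the dedicated MRI.

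A reader might infer that the study cannot reach its target. The documents do not show that: the correction raises the yield, and uptake is simply unstated.

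The conclusion assumes that 50% is the rate of consent to MRE review, as the sentence says, and that the two cited prevalences apply. It takes the minimum of more than 60 as printed. That minimum cannot be uniquely reproduced, because 8.1 gives no null or comparator sensitivity, so the required rates are only as firm as that threshold.

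**What to change.** In 8.1:

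- (a) Correct 445 to 495, or state the extra first-stage factor that gives 445. If 445 is kept, recompute the figures in (b) from it.
- (b) Replace the statement that at least 66 cases will be recruited with the expected number of MRE-positive patients: about 74 to 83 from 495 scans at 15% to 16.7%. State an assumed combined rate of second consent and MRI completion, allowing for cases who will have the MRI as standard of care. Note that about 74% to 82% is needed to keep more than 60 cases, so that the margin is shown as conditional on that rate.
- (c) As a clarification of wording, describe the 1100 consistently as scans or as CD patients in 8.1, 1.5, 4.1 and 5.2.1.1.

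The cost is one reworded paragraph and an aligned description in three other sections. No patients or procedures are added. The one drawback for the authors is that the margin over 60 is no longer unconditional.
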